**Table 1-2. Schedule of Pharmacokinetic Samples**

	Time Points Relative to Dosing								Notes	
	Predose	During Infusion	After EOI							
	Within 4 h Prior SOI	10 m Before EOI	5 m	0.5 h	1 h	2 h	3 h	4 h		
Window			± 1 m	± 5 m	± 5 m	± 5 m	± 10 m	± 10 m		
Part 3										
C1D1	X	X	X	X	X	X	X	X	If an MT-3724 dose is rescheduled, then the PK samples planned per protocol for that dose should be drawn on the new dosing day. For example, if Dose 6 is delayed from D12 to D14, then the PK samples planned for D12 should be drawn on D14. Unscheduled assessments may be performed at any time at the investigator's discretion.	
C1D3	X	X	X	X	X	X				
C1D12	X	X	X	X	X	X				
CXD1	X	X	X							
Part 4										
C1D1	X	X	X	X	X	X	X		Samples for PK must be drawn from a different line than that used for MT-3724 administration.	
C1D3	X	X	X			X				
C1D12	X	X	X			X				
CXD1	X	X	X							

C = cycle; D = day; PK = pharmacokinetics, SOI = start of infusion; EOI = end of infusion.

## 2 INTRODUCTION

### 2.1 Background

#### 2.1.1 Advanced Stage Cancer Patient Population

Starting with Amendment 9.0 (expansion cohort), Parts 3 and 4 will enroll subjects with relapsed or refractory (r/r) large B-cell lymphoma after 2 or more lines of systemic non-Hodgkin Lymphoma (NHL) therapy and who are not eligible to receive candidates for curative therapy. See [Section 5](#) for all eligibility criteria.

#### 2.1.2 Epidemiology, Classification, and Treatment Standards

**Non-Hodgkin's Lymphomas:** The 2019 SEER database estimated 74,200 patients in the United States (US) would be diagnosed with NHL, or approximately 26,000 people with diffuse large B-cell lymphoma (DLBCL) or approximately 7.8/100,000 ([Howlader, 2019](#)). Amongst B-cell NHL subtypes, DLBCL is the most frequent at approximately 36%, according to the SEER data base. Rates, however, vary by region. In the United Kingdom, the annual incidence of DLBCL is 8.5/100,000 ([HMRN, 2020](#)) yet across Europe, the incidence is reported to be approximately 3.8/100,000 ([Vitolo, 2016; Møller, 2004](#)) possibly reflecting differences in genetic and environmental risk factors. This latter figure is similar to the incidence of DLBCL in Australia (approximately 2/100,000) ([NCCI, 2020](#)). In Taiwan, the incidence of DLBCL is approximately 3/100,000 ([Ko, 2018](#)), in South Korea, China and Japan, approximately 3.8/100,000 ([Yoo, 2018; Miyoshi, 2018; Sun, 2012](#)).

Lymphoma includes a heterogeneous group of malignancies originating from lymphoid tissues (mainly of lymph nodes) with different biology and prognoses divided into 2 large groups of neoplasms: (1) non-Hodgkin's lymphoma and (2) Hodgkin's disease. Various neoplastic malignant cell lines correspond to each of the cellular components of antigen stimulated lymphoid follicles. Almost 85% of NHLs are of B-cell origin; only 15% are derived from T-cells or Natural Killer cells, and the small remainder arises from macrophages.

Non-Hodgkin Lymphoma represents a progressive clonal expansion of a lymphoid cell line arising from an accumulation of lesions affecting proto-oncogenes or cancer suppressor genes, resulting in cell immortalization. Although a variety of laboratory and imaging studies are used in the evaluation and staging of suspected NHL, a well-processed section of an excised lymph node is the mainstay of pathologic diagnosis. NHL subtypes are characterized by the level of differentiation, the size of the cell of origin, the originating cell's rate of proliferation, and the histologic pattern of growth. Several cytogenetic lesions are associated with specific NHLs, reflecting the presence of specific markers of diagnostic significance in sub-classifying various NHL subtypes.

Non-Hodgkin Lymphoma includes many clinicopathologic subtypes, each with a distinct epidemiology, etiology morphology, immunophenotype, genetic features, clinical characteristics and response to therapy. For many of the B-cell NHL subtypes, the pattern of growth and cell

size may be important determinants of NHL tumor aggressiveness. Non-Hodgkin Lymphoma tumors that grow in a nodular pattern are generally less aggressive than lymphomas that proliferate in a diffuse pattern. Lymphomas of small lymphocytes generally have a more indolent course than those of large lymphocytes, which may have intermediate-grade or high-grade aggressiveness. However, some subtypes of high-grade lymphomas are characterized by small cell morphology.

The treatment of B-cell NHL varies greatly, depending on tumor stage, grade, and type as well as several clinical factors. The 5-year relative survival rate of patients with NHL is approximately 63%. The survival rate has steadily improved over the last 2 decades, due to improvements in medical and nursing care, the advent of monoclonal antibodies (mAbs), including CD20-targeting therapies, validation of biomarkers of response, and the implementation of tailored treatment.

### 2.1.3 Anti-CD20 mAb Therapy for Non-Hodgkin Lymphoma

Anti-CD20 mAb therapy has become a ubiquitous component of treatment regimens for B-cell malignancies. Clinically active anti-CD20 mAbs used for the treatment of NHL can be separated into 2 types based on cellular effects observed on binding to CD20-expressing B-cells. Type I antibodies (rituximab and ofatumumab) induce redistribution of CD20 into large lipid rafts in the plasma membrane and have strong complement-dependent cytotoxicity (CDC) and antibody-dependent cell-mediated cytotoxicity but have minimal direct antitumor effects. Type II antibodies (tositumomab and obinutuzumab) do not induce redistribution of CD20, have minimal CDC, strong antibody-dependent cell-mediated cytotoxicity and increased direct antitumor effects. Although fully humanized mAbs should be less immunogenic than the chimeric rituximab, none of the more recently approved anti-CD20 antibodies appears to be clinically more effective against NHL in direct comparisons, perhaps because of patients' baseline immune status ([Maloney, 2012](#)).

A multinational retrospective study (SCHOLAR-1) analyzed overall response rate (ORR) and overall survival (OS) in 636 patients with r/r NHL including DLBCL, follicular lymphoma (FL) and primary mediastinal B-cell lymphoma (PMBCL) based on 2 Phase 3 trials (LYSA/CORAL, CCTG/LY.12) and 2 observational cohorts from MD Anderson and University of Iowa/Mayo Clinic (Crump 2017). For patients with refractory (refractory included patients who relapsed early ie, within 12 months of stem cell therapy) DLBCL, ORR was 26% (CR 7%) to next line therapy, and OS was 6.3 months, with 2-year survival rate of 20%. Overall response rate in patients relapsing after 2nd line therapy was 26% (CR 10%). Response significantly correlated with survival, especially when patients were able to proceed to stem cell therapy thereafter thus emphasizing the importance of novel salvage treatments.

Most patients across all types of NHL eventually become refractory to all anti-CD20 mAb treatments. There are several mechanisms by which this can happen, including increased mAb catabolism, initial development or post treatment selection of malignant cells with low levels of surface CD20 expression, resistance to mAb effector mechanisms and/or impaired immune cell function ([Tedder, 1988](#)). It has also been shown that anti-CD20 mAbs induce internalization of CD20 by malignant cells, where the degree of internalization is higher with Type I anti-CD20

mAbs ([Beers, 2010](#)). The internalization requires the binding of the fragment crystallizable region (Fc) tail of the mAb to the Fc $\gamma$  receptor IIb (Fc $\gamma$ RIIb) on the malignant B-cell. Differential Fc $\gamma$ RIIb expression has been correlated with resistance to anti-CD20 therapy in different types of B cell malignancies ([Lim, 2011](#)). CD20 can also be removed from the B-cell surface following the molecular reorganization known as trogocytosis, which occurs during the conjugation between the Fc $\gamma$  receptor on B-cells and the antigen-presenting immune cells ([Beum, 2011](#)). Further, due to their relatively large size, typically, less than 0.01% of the injected dose of an anti-CD20 mAb localizes to NHL tumors in human subjects ([Milenic, 1991](#)).

## 2.2 Molecular Templates Investigational Product Background: MT-3724

MT-3724 is a recombinant homodimeric fusion protein. Each monomer consists of a single chain variable fragment (scFv) with affinity for human CD20 cell surface protein fused to the enzymatically active Shiga-like toxin-I A1 subunit (SLT-I A1). The primary structure of MT-3724 is a single polypeptide chain consisting of 512 amino acids of an approximate molecular weight of 55 kiloDaltons (kDa) (data on file). The theoretical molecular weight of the MT-3724 homodimer is ~ 110.4 kDa. MT-3724 has been shown to specifically bind and kill CD20-expressing malignant B-cells ([Rajagopalan, 2013](#)).

As a direct-kill immunotoxin directed against CD20, MT-3724 could achieve malignant cell lysis in refractory or relapsed NHL regardless of the biologic variations of malignant B-cells or patient's immune status. The smaller size of MT-3724 may offer an advantage over anti-CD20 mAbs enabling better tumor penetration. The scFv in MT-3724 binds to a CD20 epitope within rituximab's binding domain. While able to bind to CD20, the scFv in MT-3724 lacks an intact Fc region and does not rely on host antibody-directed cytotoxicity or CDC to induce cell death. The scFv in MT-3724 should not be adversely impacted by reduction of CD20 B-cell expression via internalization or trogocytosis. Thus, MT-3724 could avoid, mitigate or delay the emergence of resistance to anti-CD20 mAb therapy and offer potential benefit in unmet medical need.

### 2.2.1 Summary of Clinical Experience

The clinical development program for MT-3724 is being evaluated in 3 ongoing studies: 1 monotherapy study (MT-3724\_NHL\_001 [NHL\_001]) and 2 combination therapy studies (MT-3724\_NHL\_002 [NHL\_002] and MT-3724\_NHL\_003 [NHL\_003]) with gemcitabine and oxaliplatin (GEMOX) and lenalidomide (LEN), respectively. Further studies of MT-3724 in other subtypes of NHL are planned.

Data from the MT-3724 monotherapy study, NHL\_001, showed clinical antitumor activity in heavily pre-treated subjects with relapsed or refractory DLBCL who had low serum level of rituximab before the start of treatment.

Across 3 studies (NHL\_001, NHL\_002 and NHL\_003) as of 28 August 2020, capillary leak syndrome (CLS) has been reported in 5 subjects: 2 subjects from NHL\_001 dosed at 75  $\mu$ g/kg/dose, 2 subjects from NHL\_002 dosed at 10  $\mu$ g/kg/dose, and 1 subject from NHL\_003 dosed at 25  $\mu$ g/kg/dose. The maximum severity for all events was Grade 2. After the data cutoff, 1 event of Grade 5 CLS was reported in the NHL\_001 study, Part 3 dosed at 50  $\mu$ g/kg/dose. As a

result, more stringent safety measures are implemented in all MT-3724 trials including this protocol version.

Important identified risks for MT-3724 include infections (including pneumonia and viral infections), CLS, Neutropenia, and Edema and Peripheral Edema. Important potential risks include acute kidney injury, Myalgia/muscle weakness, systemic inflammatory response syndrome (SIRS)/ cytokine release syndrome (CRS), Infusion related reactions, Tumor lysis syndrome, and Reproductive risk.

Adverse events of special interest include Neutropenia, acute kidney injury, CLS, SIRS/CRS.

Please refer to the Investigator's Brochure for comprehensive information available for MT-3724 to date.

## 2.2.2 Guidance to the Investigator for Capillary Leak Syndrome

Capillary leak syndrome typically occurs during earlier cycles of treatment. Capillary leak syndrome is suspected if the subject experiences at least 2 of the following signs and/or symptoms within the same cycle (unless unequivocally related to underlying condition):

- Hypoalbuminemia
- Hypotension
- Edema (peripheral or central, all types) and/or weight gain

Subjects should be closely monitored for signs and symptoms of CLS. This includes monitoring of vital signs (temperature, heart rate, blood pressure [BP], respiration rate), body weight and edema of any type including both peripheral edema and central edema (such as pleural effusion or signs of dyspnea), and monitoring of laboratory parameters including hemoconcentration (eg, hematocrit, Hb), and especially albumin and creatine phosphokinase (CK) in case of clinical symptoms indicative of CLS.

Refer to the MT-3724 CLS management guide.

Refer to [Section 6.2](#) for dose modification guidelines.

## 3 OBJECTIVES AND ENDPOINTS

### 3.1 Part 3 Objectives and Endpoints

OBJECTIVES	ENDPOINTS
Primary	

• To evaluate the safety of MT-3724 as monotherapy in subjects with relapsed or refractory diffuse large B-cell lymphoma (DLBCL)

	

• adverse events (AE)

• laboratory abnormalities

• vital signs

Secondary	

• To evaluate the efficacy of MT-3724 as monotherapy in subjects with relapsed or

	

• Overall response rate is defined as the proportion of subjects with either a complete response (CR)

OBJECTIVES	ENDPOINTS
refractory DLBCL based on the overall response rate (ORR) by the Lugano Classification for Lymphoma (Cheson, 2014)	or a partial response (PR) as determined by independent, blinded central review

 
To evaluate additional measures of efficacy of MT-3724 as monotherapy in subjects with relapsed or refractory DLBCL
 
	
 
Overall response rate, defined as the proportion of subjects with either a CR or a PR as determined by investigator assessment
 
duration of tumor response (DOR), defined as time from initial documentation of tumor response (CR or PR) to disease progression
 
disease control rate (DCR), defined as proportion of subjects who have achieved CR, PR and stable disease (SD; defined as SD for 6 months or longer)
 

 
To evaluate the pharmacokinetics (PK) of MT-3724 as monotherapy in subjects with relapsed or refractory DLBCL
 
	
 
Pharmacokinetics parameters, where calculable, include: maximum observed plasma concentration (<math>C_{max}</math>), time to achieve <math>C_{max}</math> (<math>t_{max}</math>), and area under the plasma concentration time curve from 0 to 4 hours (<math>AUC_{0-4}</math>), AUC from 0 to infinity (<math>AUC_{0-\infty}</math>), AUC from dosing to last measurable concentration (<math>AUC_{last}</math>), half-life (<math>t_{1/2}</math>), volume of distribution (<math>V_z</math>), and clearance (CL)
 


 
To evaluate the pharmacodynamics of MT-3724 as monotherapy in subjects with relapsed or refractory DLBCL
 
	
 
B-cell count
 
Immunophenotyping
 
Circulating immunoglobulins (IgA, IgG, IgM)
 

 
To evaluate the immunogenicity of MT-3724 as monotherapy in subjects with relapsed or refractory DLBCL
 
	
 
incidence of anti-drug antibodies (ADA)
 

Exploratory	

## 3.2 Part 4 Objectives and Endpoints

OBJECTIVES	ENDPOINTS
Primary	

 
To determine the efficacy of MT-3724 as monotherapy in subjects with relapsed or refractory DLBCL based on the ORR by the Lugano Classification for Lymphoma (Cheson, 2014)
 
	
 
overall response rate is defined as the proportion of subjects with either a CR or a PR as determined by independent, blinded central review
 

Key Secondary	

 
To determine additional measures of efficacy of MT-3724 as monotherapy in subjects with relapsed or refractory DLBCL
 
	
 
Duration of tumor response, defined as time from initial documentation of tumor response (complete response [CR] or partial response [PR]) to disease progression
 

Secondary	

 
To determine the safety of MT-3724 as monotherapy in subjects with relapsed or refractory DLBCL
 
	
 
adverse events
 
laboratory abnormalities
 
vital signs
 

 
To evaluate the effect of MT-3724 on the QT/QTc interval in subjects with relapsed or refractory DLBCL
 
	
 
electrocardiograms (ECGs)
 
adverse events suggestive of cardiotoxicity
 

 
To determine additional measures of efficacy of MT-3724 as monotherapy in subjects with relapsed or refractory DLBCL
 
	
 
overall response rate, defined as the proportion of subjects with either a CR or a PR as determined by investigator assessment
 
disease control rate (DCR), defined as proportion of subjects who have achieved CR, PR and SD (defined as SD for 6 months or longer)
 
progression-free survival (PFS), defined as the time from study enrollment to the earliest date of disease progression or death from any cause
 
overall survival (OS), defined as the time from study enrollment to death from any cause
 


 
To determine the pharmacokinetics (PK) of MT-3724 as monotherapy in subjects with relapsed or refractory DLBCL
 
	
 
Pharmacokinetics parameters, where calculable, include: <math>C_{max}</math>, <math>t_{max}</math>, <math>AUC_{0-4}</math>, <math>AUC_{0-inf}</math>, <math>AUC_{last}</math>, <math>t_{1/2}</math>, <math>V_z</math> and <math>CL</math>
 

 
To determine the pharmacodynamics of MT-3724 as monotherapy in subjects with relapsed or refractory DLBCL
 
	
 
B-cell count
 
Immunophenotyping
 
Circulating immunoglobulins (IgA, IgG, IgM)
 

 
To determine the immunogenicity of MT-3724 as monotherapy in subjects with relapsed or refractory DLBCL
 
	
 
incidence of ADA
 

Exploratory	

OBJECTIVES	ENDPOINTS

The DLT assessment period is 21 days. DLTs will be assessed during Cycle 1 of each enrolled dose cohort.

Starting with enrollment into Cohort 1, a minimum of 6 eligible subjects will be enrolled into 1 of 2 predefined sequential dose cohorts, unless precluded by DLTs. Each dose cohort is deemed intolerable if 2 or more DLTs occur at any time in Cycle 1.

If permitted by the safety results, the MT-3724 dose escalation is planned to proceed in sequential dose cohorts. Before each dose escalation decision, the sponsor, investigators and independent pharmacovigilance physician will review all available data in the current dose cohort. The safety management team must decide by consensus whether it is safe to proceed to the next planned dose level, or to another dose not pre-specified in the protocol.

#### **4.1.1.1      Subject Evaluable for Dose Decisions**

Subjects in Part 3 will be evaluable for dose decisions if they satisfy one of the following criteria:

- Have had a DLT after at least one dose of MT-3724 in Cycle 1; or
- In the absence of toxicities that have delayed or caused omission of doses, subjects have received at least 4 of 6 (67%) doses of MT-3724 within 21 days

Subjects who are not evaluable for dose decisions will be replaced.

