### **Cohort 1:**

The starting MT-3724 dose for each subject will be 10 µg/kg for the first 2 doses (D1, D3) and then increased to 25 µg/kg for the remaining doses (D5, D8, D10, D12) of the first 21-day cycle and all doses of Cycle 2 (D1, D3, D5, D8, D10, D12). Dosing will then continue at 25 µg/kg weekly (D1, D8, D15), beginning with Cycle 3 ([Table 6-1](#)).

If fewer than 2/6 subjects have a DLT in Cohort 1, then the study will proceed to Cohort 2. If 2 or more subjects have a DLT in Cohort 1, the study will be stopped.

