#### **8.5.1 Time Period and Frequency for Collecting Adverse Event Information**

The AE reporting period will begin on the day of the first dose of study drug unless deemed related to a protocol screening procedure after signing informed consent until the STFU visit or phone call, or until the start of new cancer therapy (unless the investigator believes the AE is related to MT-3724), whichever occurs first.

Grade  $\geq$  2 AEs related to MT-3724 that are ongoing at the STFU Visit should be followed by the investigator until all events have resolved to Grade  $\leq$  1.

Those AEs that occur after the first dose on C1D1 will be considered treatment-emergent.

All AEs that occur in enrolled subjects during the AE reporting period specified in the protocol must be recorded, regardless of the relationship of the AE to MT-3724. Any serious known untoward event that occurs beyond the AE reporting period that the investigator assesses as at least possibly related to MT-3724 should also be reported to the sponsor.

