All subjects will receive a single course of study drug via a 2 (\pm 15 minutes) IV infusion of MT-3724 on Days 1, 3, 5, 8, 10 and 12. Each dose of MT-3724 will be at the adjusted MTD (50 mcg/kg/dose). Three subjects were started in Part 2 at 75 mcg/kg/day but later had possibly related TEAEs that required dose reduction or a treatment discontinuation. Following the first dose in each cycle, there will be a minimum 21-day observation period for each subject prior to initiating the next treatment cycle. Subjects experiencing a serious adverse event (SAE) attributable to MT-3724 may be withdrawn from the study or depending upon the nature of the

event, the Investigator, in consultation with the DMC, may, once the event has resolved, resume dosing at a dose reduced by 25-33%. Subjects will have successfully completed a cycle if they receive at least 4 of the 6 infusions in that cycle, and they are followed for 21 days after their first dose in that cycle. If a subject completes less than 4 of the 6 infusions in the first 12 days of a cycle and the missed infusions were not due to an event that would contraindicate further dosing, then the Investigator in consultation with the Sponsor may attempt to achieve a minimum of 4 infusions by administering the missed doses in the third week (Days 15 - 19) of that cycle. In such instances, subjects must still be observed for a minimum of 21 days following the first dose in Cycle 1 prior to initiating any further study drug dosing. No dose escalation will be permitted above the adjusted MTD (50 mcg/kg/dose) identified by the DMC. However, at the Investigator's discretion, the dose for any subject in the Part 2 expansion cohort may be reduced by 25-33% for one or more doses in any cycle (see below) based upon a subject's response at the adjusted MTD (50 mcg/kg/dose).

Subjects must receive a minimum of 4 of the 6 infusions in a cycle in order to successfully complete that cycle and continue in the study. For subjects in Parts 1 and 2 who complete **at least 4** of the 6 infusions in any cycle, and the missed infusions were not due to an MT-3724-related event that contraindicates further dosing (see above for criteria for continued dosing), then up to 5 total cycles may be administered on the same schedule (Days 1, 3, 5, 8, 10 and 12) and at the same dose (as long as that dose is not subsequently identified to be a toxic dose).

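### Part 3 dose-decision evaluability rests on dose count alone: a subject lost after dose 4 for a non-toxicity reason stays in the 2-of-6 denominator without completing the 21-day DLT period

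*Protocol*

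**What the plan says.** Protocol Section 4.1.1 fixes the window: "The DLT assessment period is 21 days. DLTs will be assessed during Cycle 1 of each enrolled dose cohort". It calls a cohort intolerable when two or more DLTs occur at any point in Cycle 1. Before escalation, the sponsor, the investigators and an independent pharmacovigilance physician review the available data.

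Section 4.1.1.1 then defines who counts: "Subjects in Part 3 will be evaluable for dose decisions if they satisfy one of the following criteria". The first criterion is a DLT after at least one Cycle 1 dose. The second opens with "In the absence of toxicities that have delayed or caused omission of doses" and requires that "subjects have received at least 4 of 6 (67%) doses of MT-3724 within 21 days". Sections 4.1.1.1 and 7.2 replace subjects who are not evaluable for dose decisions.

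Section 6.1.1.2 applies the count: "If fewer than 2/6 subjects have a DLT in Cohort 1, then the study will proceed to Cohort 2". With two or more DLTs in Cohort 1 the study stops. In Cohort 2 the same threshold decides which regimen goes into Part 4. Cycle 1 doses are scheduled for Days 1, 3, 5, 8, 10 and 12, each with a one-day allowance (Section 6.1.1.3).

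**The concern.** The 21 days in Section 4.1.1.1 limit when the doses are given, not how long the subject is watched. A subject without a DLT therefore meets the second criterion at dose 4, and nothing later in the cycle can make that subject non-evaluable. If the subject then leaves for a reason other than toxicity, the unobserved remainder of the window is counted as DLT-free.

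Three exits are plausible in relapsed or refractory DLBCL:

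- withdrawal of consent with objection to further data collection;
- loss to follow-up;
- progression followed by new therapy.

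The count decides whether the study stops, opens Cohort 2 or fixes the Part 4 regimen, and it follows a Grade 5 capillary leak event in Part 3 (Section 2.2.1). A missed DLT can turn a failing cohort into a passing one. Missing observation cannot work in the other direction.

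**Working it through.** **The plan's own figure.** 4/6 = 66.7%, which agrees with the stated 67%. The documents give no error rate for the 2-of-6 rule, no expected DLT rate and no onset distribution, so there is nothing further to reproduce.

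**Share of the window at dose 4.** Day 8 is 8/21 = 38%. The one-day allowance gives 7/21 = 33% to 9/21 = 43%. One subject is 1/6 = 17% of the cohort.

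**What can be missed after Day 8.** Doses 5 and 6 fall on Days 10 and 12. Several DLTs in Section 10.3.9 need laboratory tests or time to qualify. Grade 4 neutropenia must last more than 5 days (absent early G-CSF), so neutropenia starting on Day 8 cannot meet the duration criterion before Day 13. A Grade 3 or higher electrolyte abnormality must remain unresolved at 72 hours. Transaminase and bilirubin criteria need blood tests.

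**Effect on the decision (illustrative).** Assume a true 21-day DLT risk p = 0.33, independent across subjects. Let q be the risk actually observed in a subject lost at Day 8. A cohort passes with at most 1 DLT in 6.

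- Full follow-up: 0.67^6 + 6 × 0.33 × 0.67^5 = 0.0905 + 0.2673 = 0.358.
- One subject lost: (1 − q)(A0 + A1) + q·A0, with A0 = 0.67^5 = 0.1350 and A1 = 5 × 0.33 × 0.67^4 = 0.3325.
- Two lost: (1 − q)²(B0 + B1) + 2q(1 − q)·B0, with B0 = 0.67^4 = 0.2015 and B1 = 4 × 0.33 × 0.67^3 = 0.3970.

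| Assumed onset | q | None lost | One lost | Two lost |
|---|---|---|---|---|
| Even spread, q = 0.33 × 8/21 | 0.126 | 0.358 | 0.426 | 0.502 |
| Constant hazard, q = 1 − 0.67^(8/21) | 0.141 | 0.358 | 0.420 | 0.490 |
| 70% of risk by Day 8 | 0.231 | 0.358 | 0.391 | 0.426 |
| 80% of risk by Day 8 | 0.264 | 0.358 | 0.380 | 0.403 |

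Under constant hazard, a 20% risk gives 0.655, 0.704 and 0.752 for none, one and two lost. A 50% risk gives 0.109, 0.151 and 0.207.

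**The case against.** The best reply is that the protocol already follows most of these subjects past Day 21. Stopping after a Day 8 dose leads to an end-of-treatment visit within 14 days of that dose and a safety visit 30 ± 3 days after it, around Day 38 (Sections 8.1.3 and 8.1.4). A reader might infer from Section 8.5.1 that new therapy simply ends adverse event collection. It does not: collection runs to the follow-up contact "or until the start of new cancer therapy (unless the investigator believes the AE is related to MT-3724), whichever occurs first", and a DLT must be at least possibly related to MT-3724. This stands, and it narrows the gap. It does not close it. Subjects who withdraw and object to data collection are excepted from both visits, and a subject lost to follow-up cannot be assessed. After new therapy the safety contact may be a telephone call that records only adverse events and concomitant medications (Schedule of Activities footnote e). A call supplies no protocol laboratory data for the laboratory-based criteria.

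A second reply is that toxicity-related dose loss is already handled by the opening condition of the second criterion. That is correct, but progression and withdrawal fall outside it.

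Third, the Version 11 rationale in Section 12.1 reports that capillary leak events came within a few days of initial dosing or re-dosing. This supports the smaller figures in the lower rows of the table. It says nothing about other DLTs, and it predates the step-up regimen, in which Cohort 2 first reaches 50 µg/kg on Day 10.

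A reader might also infer that the sponsor once had a two-part DLT-evaluability rule and dropped half of it. The SAP does pair 4 of 6 infusions with a follow-up condition (for Part 2, "and they are followed for 21 days after their first dose in that cycle"; for Part 1, 28 days). Those sentences define completing a cycle or the Core Study, not DLT evaluability.

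**Conclusion.** The concern holds in a limited form. As written, a subject without a DLT who leaves after dose 4 for a non-toxicity reason remains among the six and is not replaced, although the window was not completed. The direction of the bias is certain. Its size is not: at an assumed 33% risk, one such subject adds between about 2 and 7 percentage points to the chance of passing, and two add about 4 to 14, depending on how early DLTs occur. No passage says how often such losses will happen. One or two in six is a working assumption.

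Two stronger readings are not supported. Section 4.1.1.1 does not declare anyone DLT-free at Day 8, because DLTs in subjects still under observation count throughout Cycle 1. Nor do the documents permit the cohort decision as soon as the sixth subject receives dose 4. The threshold refers to an outcome over a stated 21-day period, and escalation needs a consensus review of the data. The text does fail to say that this review waits until all six have completed the period, and that should be made explicit.

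This should be corrected before the first cohort decision. It is a gap in a definition, not a flaw in the dose-finding design.

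**What to change.** Reconcile Section 4.1.1.1 with Section 4.1.1. A subject without a DLT would be evaluable only if the existing dose minimum is met and the subject was observed, with the scheduled safety assessments, through the end of the protocol's own 21-day DLT period. Any other subject without a DLT would be non-evaluable and replaced under Section 7.2. In Section 6.1.1.2, state that the 2-of-6 count is read when all six evaluable subjects have had a DLT or completed that period.

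No dose, DLT criterion or threshold changes. The SAP completion rules for Parts 1 and 2 show that pairing a dose count with a follow-up period is workable. The cost is a sentence or two in each section, possibly one or two replacement subjects within the approximately 25 planned, and a short wait before each cohort decision. That wait is at most 21 − 8 = 13 days after the last subject's dose 4, plus the time to observe any replacement.
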